10.6 Handling of Missing Data

Under the ITT principle, all subjects who are randomized are included in the analysis. Therefore, missing data, especially in the outcome measures, can be problematic. For the primary outcome analysis, missing data are imputed by assuming the worst-case scenario. In other words, subjects with a missing score for both of the assessments (mRS and NIHSS) at 3 months are assigned an unfavorable outcome. Of course, missing data due to death are scored as unfavorable outcome. If a subject is missing one of the assessments and the observed outcome is unfavorable (i.e., NIHSS score ≥ 2 or mRS score ≥ 2), the subject is assigned an unfavorable outcome. On the other hand, if the subject is missing one of the assessments and the observed outcome is favorable (i.e., NIHSS score of 0 or 1 or mRS score of 0 or 1), the subject is assigned a favorable outcome, per the definition of the primary outcome.

As a secondary analysis approach, the primary efficacy outcome is imputed using other methods (e.g., last observation carried forward from the 1 month mRS and discharge NIHSS assessments; hot-decking; logistic regression), and sensitivity analysis is conducted. Similar imputation methods are employed for secondary outcomes that are binary. For measurements that are on a continuous scale (e.g., SSQOL), the multiple imputation method is employed. Missing covariate data are imputed using either the multiple imputation or regression method, if needed.

It is possible and probable that missing outcome data may not be missing at random, in which case the imputation methods to be employed may yield biased results. However, based on our previous experiences with clinical trials of acute stroke, we anticipate minimal lost-to-follow-up for the 3-month assessment (less than 5%) of the primary outcome. The concern, therefore, is on the outcomes assessed at 1 year. All efforts must be put forth to ensure near-complete follow-up, in particular with occurrences of deaths and recurrences of stroke events. A forum, such as the ALIAS Trial Newsletter and Trial website, is established by the Executive Committee to allow communications among the clinical sites to share what methods are most successful in minimizing lost-to-follow-up cases.

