Study Sites	
 • University of Miami (Study Chair Site and Fiscal Management Office) • SDCC at MUSC (Data and Project Management and Statistics Center) • University of Calgary (Canadian Coordinating Center) • Approximately 100 clinical centers in US, including sites from the Neurological Emergencies Treatment Trials (NETT) Network, Canada, and possibly other countries
Study Period	Planned enrollment period – 3 years Planned duration of the study – 4 years
Study Population	Acute ischemic stroke patients.
Primary Study Objective	To ascertain whether high-dose human albumin (ALB) therapy confers neuroprotection in acute ischemic stroke over and above best standard of care. (Specifically, to determine whether ALB therapy increases the proportion of acute ischemic stroke patients with favorable outcome compared to placebo therapy at 3 months from randomization.)
Secondary Study Objectives	
To evaluate:
 
 • overall clinical outcome (as assessed by the global statistical test of NIHSS, mRS, and BI scores) at 3 months post-randomization. • overall clinical outcome as assessed by the full scale of the modified Rankin scale. • neurological outcome as assessed by NIHSS score at 3 months post-randomization. • functional outcome as assessed by mRS and BI at 3 months post-randomization. • quality-of-life as assessed by EuroQol at 3 months and 1 year post-randomization, and by Stroke-Specific Quality of Life (SSQOL) instruments at 3 months post-randomization. • robustness of ALB therapy as measured by a favorable

	
outcome of mRS of 0 or 1 at one year post-randomization.
 
 • incidence of recurrent ischemic stroke within 1 month, 3 months and 1 year post-randomization, as assessed by Questionnaire to Validate Stroke-Free Status (QVSFS). • mortality within 3 months and 1 year post-randomization. • incidence of symptomatic ICH within 24 (\pm 6) hours of randomization. • cognition measured at 3 months by Trailmaking A and B.
Study Design	The ALIAS Trial consists of a multicenter, randomized, double-blind, parallel group, two-arm Phase III trial of ALB therapy in patients with acute ischemic stroke.
Sample Size	Approximately 1100 subjects are randomized in a 1:1 ratio to IV treatment of either ALB or placebo saline solution.

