10.5 Analysis Samples

As the primary analysis, all futility and efficacy outcome measures specified in Sections 10.2.1 and 10.2.2 are analyzed under the ITT principle. For the outcomes measured at 3 months, the ITT sample includes all subjects who are randomized regardless of whether they actually received the study drug (ALB or placebo), and regardless of whether or not they had a 3-month outcome assessments. If they are missing, their data are imputed. See Section 10.6 for handling of missing data.

As secondary analyses, the 3-month outcome assessments may be analyzed excluding those who are lost-to-follow-up (LTFU) only if the proportion of LTFU is greater than 5%. If it is less than 5%, we anticipate that the analysis results with the excluded sample will differ minimally from the ITT sample. We also anticipate the possibility, albeit very small, of subjects receiving the incorrect treatment. This is considered a major protocol violation (PV). Nevertheless, as a tertiary analysis of outcome measures, we will repeat the analysis using this “as treated” sample upon completion of the Trial.

Any randomized subjects who received at least 20% of their weight-based dose of the study drug are included in the safety analysis sample.

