10.7.2 Statistical Stopping Guidelines for Safety

Because of concerns about excess deaths in one group over the other in Part 1 of the ALIAS Trial, we have established one set of statistical safety stopping guidelines based on mortality within 30 days from randomization as shown in Table 10.7.2.

Table 10.7.2 Suggested approximate stopping guidelines for safety.

Approximate N at interim monitoring*	Total # death*	Maximum split in # of death between the two groups to yield LL of 99% CI on RR < 1.0		Unadjusted RR**	LL of 99% CI for the unadjusted RR
		Group A	Group B		
100	15	3	12	4.00	0.959
200	30	9	21	2.33	0.981
300	45	16	29	1.81	0.925
400	60	22	38	1.73	0.969
500	75	29	46	1.59	0.952
600	90	35	55	1.57	0.986
700	105	42	63	1.50	0.977
800	120	49	71	1.45	0.972
900	135	55	80	1.45	0.998
1000	150	62	88	1.42	0.994
1100	165	69	96	1.39	0.991

* Assumes 15% overall 30-day death rate.

** In practice, the RR will be estimated adjusting for thrombolysis treatment, age, and baseline NIHSS, and its LL of the 99% CI will be used for stopping criterion.

The above stopping guideline is based on the total number of deaths observed within 30 days. Hence, the first interim monitoring point occurs after a total of 15 deaths are observed, which should translate to when approximately 100 subjects have had the 30-day follow up, assuming a 15% overall 30-day death rate. The 3-to-12 split of the 15 deaths yields an unadjusted RR of 4.0 with the lower limit (LL) of its one-sided 99% CI at just below 1.0. The split that is more extreme (i.e., 2-to-13, 1-to-14, or 0-to-15) will yield an LL of greater than 1.0.

Subsequent interim monitoring point occurs after every additional 15 deaths (within 30 days) are observed.

Because thrombolysis treatment, age, and baseline NIHSS are strong prognostic indicators of death, in practice, we will estimate the RR adjusting for these covariates, and we would become alerted if the LL of its one-sided 99% CI begins to approach 1.0. The DSMB will evaluate this and other pertinent data to consider stopping the trial. It would be the DSMB's prerogative to consider all information made available to them in their decision to continue or stop the trial regardless of the above suggested statistical stopping guideline.

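### Sections 10.5 and 10.6 prescribe multiple imputation of continuous secondary outcomes in all randomized subjects without excepting deaths, so subjects who died would receive survivor-modelled scores

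*Protocol*

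**What the plan says.** Protocol section 10.5 states the scope: "all futility and efficacy outcome measures specified in Sections 10.2.1 and 10.2.2 are analyzed under the ITT principle". Section 10.2.2 lists the secondary outcomes, among them SSQOL, EuroQol, NIHSS, Barthel Index and Trailmaking. For outcomes measured at 3 months, section 10.5 includes randomized subjects "regardless of whether or not they had a 3-month outcome assessments. If they are missing, their data are imputed", and it sends the reader to section 10.6 for the method.

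Section 10.6 opens with the same principle: "Under the ITT principle, all subjects who are randomized are included in the analysis". It then sets rules for the primary outcome, among them: "Of course, missing data due to death are scored as unfavorable outcome". For continuous measures it gives one sentence: "For measurements that are on a continuous scale (e.g., SSQOL), the multiple imputation method is employed". That sentence draws no line between a score missing because the subject died and one missing because the subject was lost to follow-up.

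The safety table in section 10.7.2 carries the footnote "Assumes 15% overall 30-day death rate". Section 10.6 expects loss to follow-up at 3 months to stay under 5%.

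**The concern.** Multiple imputation in its usual form fills a missing score with a draw from a model fitted to subjects who have one. For a living subject who missed the visit, that estimates a score that exists. A subject who died before month 3 has no score to estimate, so the model supplies the score the subject might have had as a survivor with the same baseline features.

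If deaths were rare or certain to be balanced, little would follow. Neither holds here. The plan assumes a substantial death rate, and section 10.7.2 explains that the safety guideline exists because of concern about excess deaths in one group in Part 1. If one arm loses more subjects, the quality-of-life comparison would be made as though the extra deaths had been survivors, and the arm with more deaths would carry no penalty for them. Quality of life is a stated secondary objective and will be read beside the mortality results.

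**Working it through.** **Inputs from the protocol.** Total sample 1,100, randomized 1:1, so 550 per arm (synopsis, section 10.3). Overall 30-day death rate 15% (section 10.7.2). Loss to follow-up at 3 months under 5% (section 10.6). Last row of Table 10.7.2: 69 and 96 deaths, RR 1.39, lower limit 0.991.

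**1. The plan's own figures reproduce.**
- Deaths by day 30: 0.15 × 1,100 = 165, as in the table's last row.
- RR = 96/69 = 1.391.
- SE of log RR = √(1/69 − 1/550 + 1/96 − 1/550) = 0.146.
- One-sided 99% lower limit = 1.391 × exp(−2.326 × 0.146) = 0.991, as printed.

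The limit is below 1, so this split does not cross the safety guideline. A trial could reach its end with such an imbalance.

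**2. Deaths against losses.**
- Losses: at most 0.05 × 1,100 = 55, if the expectation holds.
- Ratio: 165/55 = 3.
- Share of deaths among these two sources: 165/(165 + 55) = 75%.

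Deaths between day 30 and the 3-month visit would add to the 165; the protocol gives no rate for them. Survivors unable to complete an instrument are another source of missing scores, also without a figure, so 75% is not a share of all missing scores.

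**3. Effect on a score, simple form.** Assume a 0-1 scale, a survivor mean of 0.70 in both arms, and 69 versus 96 deaths.
- Surviving fractions: 481/550 = 0.8745 and 454/550 = 0.8255.
- Death scored 0: 0.70 × (0.8255 − 0.8745) = −0.034, against the group with more deaths.
- Deaths imputed from survivors: 0.70 − 0.70 = about 0.

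**4. Effect by simulation.** Assumed: a score with mean 50 and SD 20, correlation 0.5 in size with a baseline severity covariate, deaths more likely at higher severity, and no treatment effect on the score. Each of 300 runs used 20 imputations from a normal regression on arm and the covariate. Mean differences, second arm minus first:

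| Deaths | Imputed | Survivors only | Death = 0 |
|---|---|---|---|
| 82 vs 83 | 0.1 | 0.1 | 0.0 |
| 69 vs 96 | 0.0 | +0.5 | −2.1 |

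With even deaths the three agree. With uneven deaths, imputation returns about zero. The survivors-only result leans slightly towards the arm with more deaths, because that arm's survivors are the less severe cases.

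**5. No other passage removes the problem.** The alternative sample in section 10.5 drops only subjects lost to follow-up, and only if they exceed 5%. Section 9 lists death and loss to follow-up as separate ways of leaving the trial, so deaths stay in that sample too.

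**The case against.** The strongest reply is that the imputation rules were meant for loss to follow-up. Section 10.6 names missingness from death as its own category, and it sizes the 3-month problem only by losses of under 5%. On that reading death is a known outcome and the defect is an unstated exception. Sections 10.2.2 and 10.4.2 also leave the detail of each secondary outcome to the SAP, which is not at hand and may assign a value to death. This shows what the authors may have intended, but it does not change the text. The death rule stands among rules for a favorable or unfavorable classification and cannot be applied to a continuous score. Section 10.6 does not merely defer: it names a method, and a SAP rule for deaths would have to depart from that sentence.

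Three other objections stand and limit the point.
- A reader might infer that the rule hides a mortality difference. It does not. Thirty-day death is the primary safety outcome, with an adjusted Cox model (sections 10.2.3, 10.4.3) and review after every 15 deaths (section 10.7.2). Deaths at 30 and 90 days are monitored by group (section 8.8), mortality at 3 months and 1 year is a secondary objective (section 1.2), and death is unfavorable in the primary outcome.
- A reader might infer that NIHSS, EuroQol and Trailmaking scores would also be imputed for the dead. Section 10.6 names only SSQOL, as an example, and does not class the others as continuous.
- The affected outcomes are supportive and tested at two-sided 0.01 (section 10.4.2). Effectiveness rests on the primary outcome alone (section 10.4.4), as do interim efficacy and futility decisions (section 10.7.1).

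**Conclusion.** The point holds for the continuous secondary outcomes. Sections 10.5 and 10.6 together prescribe imputation for every randomized subject with a missing score and make no exception for death. On the plan's own assumptions, deaths by day 30 alone would outnumber expected losses by about three to one, so the rule would act mainly on deaths if those were the only two sources of missing scores.

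The distortion needs an imbalance in deaths; with even deaths it is about nil. At 69 versus 96 deaths, imputation removes a difference of about 0.034 on a 0-1 scale. That figure rests on an assumed survivor mean of 0.70 and on scoring death as 0, neither of which is in the protocol. The primary analysis, the mortality analyses and the stopping guidelines are untouched. The text should be corrected because the rule is stated, the imbalance is a foreseen risk, and the correction is cheap.

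**What to change.** Change section 10.6 in two sentences. First, limit multiple imputation of continuous outcomes to subjects known to be alive at the assessment. Second, prespecify that subjects who died enter the continuous secondary outcomes as the worst outcome, for example with the worst rank and a rank-based test, and that survivors-only results are reported as descriptive. Worst rank is one of several defensible choices; what matters is that death is separated from other missingness and its handling is fixed in advance. It would also help to list which secondary outcomes count as continuous, and the SAP should carry the same rule.

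Data collection and sample size do not change. The cost is a rank-based rather than mean-based summary for these outcomes, which is harder to express in scale units.

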10.7 Data Monitoring

10.7.1 Statistical Stopping Guidelines for Overwhelming Efficacy and Futility

Three interim analyses are planned for assessment for evidence of overwhelming efficacy as well as for futility. For overwhelming efficacy, we adopt the alpha spending function approach [59], and for futility, the beta spending function approach [74]. For both overwhelming efficacy and futility, O'Brien and Fleming-type stopping guidelines are used [72]. In other words, the difference between the ALB and placebo groups must be very large early on in the study to reject the null hypothesis for overwhelming efficacy, and similarly, the difference must be very small early on in the study to "reject" the alternative hypothesis to declare futility of observing statistical differences in the treatment effect between the two groups.

The tentative stopping criteria, calculated with EAST[®] 5 software (Cytel Software, 2006), based on the 3 planned interim analyses (or a total of 4 analyses) at equal intervals during the study are provided in the SAP. These values are updated using EAST[®] 5 software. Interim analyses for consideration of stopping the study for overwhelming efficacy or for futility are based solely on the analysis of the primary outcome adjusted for thrombolysis and baseline severity. The timing and

frequency of interim analyses may be changed upon DSMB request, and the spending function approach allows for such flexibility.

Each interim analysis is conducted ignoring the interaction effect between thrombolysis and study treatment. The rationale is: (1) we expect we will have insufficient power to detect any strong qualitative interaction effect at any interim analysis; and (2) in the absence of statistical evidence of strong qualitative interaction effect, we plan to use model (2) in Section 10.4.1 as the primary efficacy analysis. However, at each interim analysis, conditional power of the test for interaction effect given the data to date and current trend will be calculated for evaluation by the DSMB.

10.7.2 Statistical Stopping Guidelines for Safety

Because of concerns about excess deaths in one group over the other in Part 1 of the ALIAS Trial, we have established one set of statistical safety stopping guidelines based on mortality within 30 days from randomization as shown in Table 10.7.2.

Table 10.7.2 Suggested approximate stopping guidelines for safety.

Approximate N at interim monitoring*	Total # death*	Maximum split in # of death between the two groups to yield LL of 99% CI on RR < 1.0		Unadjusted RR**	LL of 99% CI for the unadjusted RR
		Group A	Group B		
100	15	3	12	4.00	0.959
200	30	9	21	2.33	0.981
300	45	16	29	1.81	0.925
400	60	22	38	1.73	0.969
500	75	29	46	1.59	0.952
600	90	35	55	1.57	0.986
700	105	42	63	1.50	0.977
800	120	49	71	1.45	0.972
900	135	55	80	1.45	0.998
1000	150	62	88	1.42	0.994
1100	165	69	96	1.39	0.991

* Assumes 15% overall 30-day death rate.

** In practice, the RR will be estimated adjusting for thrombolysis treatment, age, and baseline NIHSS, and its LL of the 99% CI will be used for stopping criterion.

The above stopping guideline is based on the total number of deaths observed within 30 days. Hence, the first interim monitoring point occurs after a total of 15 deaths are observed, which should translate to when approximately 100 subjects have had the 30-day follow up, assuming a 15% overall 30-day death rate. The 3-to-12 split of the 15 deaths yields an unadjusted RR of 4.0 with the lower limit (LL) of its one-sided 99% CI at just below 1.0. The split that is more extreme (i.e., 2-to-13, 1-to-14, or 0-to-15) will yield an LL of greater than 1.0.

Subsequent interim monitoring point occurs after every additional 15 deaths (within 30 days) are observed.

Because thrombolysis treatment, age, and baseline NIHSS are strong prognostic indicators of death, in practice, we will estimate the RR adjusting for these covariates, and we would become alerted if the LL of its one-sided 99% CI begins to approach 1.0. The DSMB will evaluate this and other pertinent data to consider stopping the trial. It would be the DSMB's prerogative to consider all information made available to them in their decision to continue or stop the trial regardless of the above suggested statistical stopping guideline.

10.7.3 Data and Safety Monitoring Board (DSMB) Reports

The SDCC generates a monthly safety monitoring report as well as a comprehensive statistical report semi-annually to the DSMB. The monthly reports contain updated baseline and safety information (including statistical interim monitoring results as appropriate) by treatment-group code (A and B) but not the name of the actual treatment. If the DSMB wishes to completely unblind itself from the partially unblinded reports, the Chair of the DSMB may request the NINDS Liaison to the DSMB to open the sealed envelope that contains the treatment-code identification. This allows the DSMB to unblind itself immediately upon its decision to do so.

The semi-annual reports are distributed to the DSMB prior to their planned semi-annual meetings. The comprehensive report includes compiled data on enrollment (expected and actual), demographic and baseline characteristics, eligibility and protocol violations, safety data, concomitant medications and procedures, and data quality (e.g., timeliness of data entry, and number of data clarification requests generated and resolved). The comprehensive report that coincides in timing with the planned interim analysis also contains the results of the analysis for overwhelming efficacy and futility. The content of the reports is partially unblinded with treatment groups identified as "A" or "B". If the DSMB wishes to be completely unblinded for these comprehensive reports, a sealed treatment identification envelope will be provided to the NINDS DSMB Liaison; this envelope can be opened at the discretion of the DSMB.

11. DATA COLLECTION AND MANAGEMENT OVERVIEW

Data management is handled by the SDCC, which is housed in the Division of Biostatistics and Epidemiology in the Department of Medicine at the Medical University of South Carolina (MUSC). All activities are conducted in coordination with the clinical sites, the University of Miami and University of Calgary.

Case Report Forms (CRFs) have been developed by the SDCC with input from the Executive Committee. An electronic copy of the CRFs is made available to the clinical sites prior to initiation of the study to be used as worksheets for capturing data for the Trial.

The clinical site staff is responsible for timely entry of required data into the database via the WebDCU™ System. The WebDCU™ is a user-friendly menu-driven system with built-in warnings and rules to facilitate the data collection process and ensure sufficient quality control. Upon enrollment of an eligible subject, his/her demographics and randomization code must be entered into the database **within 8 hours** of unsealing of the subject's study medication kit (see Section 4.3.3). When a SAE is discovered, the adverse event information along with all of the data currently collected for that particular subject must be entered into the database **within 24 hours** of the discovery (see Section 8.5). All other study data must be entered **within 5 days** of each subject's completion of each

phase of the study (see Section 6.2). The details of the data entry requirements for the clinical site staff are provided in the MoP.

The study database, WebDCU™ System, has been developed in Microsoft SQL Server based on the approved CRFs. This system allows for a web-based data entry and management. The data are captured and entered (single keyed) at the clinical sites via the web interface. The data are managed (including data queries) by the SDCC using a secured ALIAS Trial website. During the design of the database, automated consistency checks and data validation rules were programmed to check for potential data errors, including missing required data, data out of pre-specified range, data conflicts and disparities within and among the CRFs. All validation rules are outlined in the Data Management Plan generated by the SDCC.

The validation procedure is implemented in two stages. First, automated data-checks flag the items that fail pre-programmed logic checks. The Study Coordinator sees on the data entry screen a validation error and he/she is requested to address it. His/her choices are to: (1) correct the entry immediately; (2) correct the entry at a later time; or (3) if the entered data are correct, dismiss the rule violation. This last option is not allowed for gross logic discrepancies such as a violation of a skip pattern. Any changes made on the website have a full audit trail. Secondly, for some checks that are more complicated, such as inter-CRF data-checks, additional validation takes place using the web interface. This process involves the running of the consistency-check (validation rules) program that was prepared during the development of the database. All data items that fail the programmed consistency checks are queried via the data clarification request (DCR) process initiated by the SDCC. The DCRs are generated, communicated between SDCC and the clinical sites, and resolved on the secured study website.

In addition to the study database, the SDCC provides the clinical site staff access (via password) to a standard set of web-enabled tools, including subject visit calendar, subject accrual reports, CRF completion status, and outstanding DCR status pertaining to their respective sites. These tools allow the staff to receive regular updates on overall study status, new external information relevant to the Trial, Committee meetings calendar, etc.

Backup tapes of data collected on the WebDCU™ System are generated on a daily basis. The backup software (logical) security policy has three main components: (1) antiviral protection with McAfee Enterprise Edition to protect all servers and workstations from infection with virus definitions, updated on a daily basis; (2) restricted access with password policies; and (3) three levels of firewall protection – MUSC dual-layered firewall (hardware) protection between the University and outside computer systems and the firewall (software) on web servers with limited access. Furthermore, the WebDCU™ System uses SSL encryption methods that allow a secured Internet transfer.

